7.3.5 Minnesota Nicotine Withdrawal Scale (revised edition) Questionnaire

The MNWS (Hughes and Hatsukami 2008) is a 24 hour recall that will be completed by the subject him/herself daily from Day 0 to Day 6, and on the second day of every visit during the ambulatory period. From Day 0 to Day 6 only, MNWS questionnaire must be asked prior to start of product use/smoking and no later than 10:00 AM. On Day 31 and Day 61 the assessment of MNWS will be conducted irrespective of the time of product use but no later than 10:00 AM. Whilst on Day 91 the assessment of MNWS has to be conducted prior to smoking but no later than 10:00 AM.

The self-reported part of the MNWS consists of the following 15 items which are rated over the last 24 hours on a scale of 0 to 4 (see Table 6). Higher scores indicate greater intensity on that scale.

The total score will be derived by calculating the average of all the non-missing data from the first 9 items. If more than 50% of the first 9 items are missing then the total score will be set to missing.

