7.8.3 Questionnaires

The subject questionnaires and the VAS used in this study will be entered by the subject directly in an electronic patient reported outcomes (ePROs) device or on paper copy. All subject reported outcome data will be provided in English and instructions will be provided in the subject's local language. The questionnaires and the VAS will be reviewed for completeness by the study collaborators and subjects will be requested to complete any missing information.

Symptoms or worsening of symptoms documented on any of the questionnaires or the VAS do not need to be documented as additional AEs because the questionnaire and the VAS will be analyzed as part of the final report. However, it is at the discretion of the Investigator to decide whether to document such symptoms as additional AEs. The main source for AE collection will be the face-to-face interview between the subject and study collaborators, using open, non-directive questions (see Section 8.2).

Data and information contained in this document are considered to constitute trade secrets and confidential commercial information, and the legal protections provided to such trade secrets and confidential information are hereby claimed under the provisions of applicable law. No part of this document may be publicly disclosed without the written consent of Philip Morris Products S.A.

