7.3.4 Modified Cigarette Evaluation Questionnaire

The MCEQ (Cappelleri et al. 2007) will be completed by the subject him/herself on a daily basis from Day -1 to Day 5 and on every ambulatory visits on Day 30 Visit (Day 30), Day 60 Visit (Day 60), and Day 90 Visit (Day 90). On Day -1 and Day 0, all subjects will complete the questionnaire. From Day 1 onwards, only subjects who are randomized to the THS 2.2 Menthol and mCC arms will complete this questionnaire.

The MCEQ consists of 12 items as presented in Table 5.

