12 PLANNED STATISTICAL METHODS

12.1 General Considerations

Data analysis will be performed using SAS[®] Version 9.3.

Data listings will be provided for all data collected as defined in the protocol, ordered by randomization arm and subject, Day, Visit and time point (if applicable), unless otherwise stated. Summary statistics and statistical analysis will only be presented for data where detailed in this SAP. All unscheduled assessments will be included in the listings.

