12.6.3.1.4 Minnesota Nicotine Withdrawal Questionnaire

The MNWS will be administered daily from Days 0 to 6, and Days 31, 61 and 91 for the assessment of Day-1 to Day 5, and Days 30, 60 and 90 as it is a 24-hour recall questionnaire.

All summaries, profiles and analysis will be presented for the day before the assessment in the THS 2.2 Menthol, mCC and SA arms.

The total score, along with the percent change from baseline will be summarized. The answers to the individual questions, along with the total score, the changes and percent changes from baseline will be listed.

The profiles of the raw means from baseline to Day 90 for the total score will be plotted.

The analysis will compare each post baseline timepoint separately for the total score. An ANCOVA model will be used with terms for baseline score, sex, and average daily mCC consumption over the last 4 weeks as reported during screening. No adjustment will be made for multiple comparisons.

The SAS code to be used is similar to the model reported in Section 12.6.1.3 "Sensitivity Analysis".

LS means for each product along with the difference (THS 2.2 Menthol - mCC) and (THS 2.2 Menthol – SA) with 95% CI will be presented in the tables.

All figures, summaries and analyses will be performed on the PP Set and the FAS only.

The data will be presented in the below outputs:

TFL number	Title
FIGURES	
15.1.2.16.1	MNWS Total Score Mean and 95% CI of Percent Change from Baseline – PP Set
15.1.2.16.2	MNWS Total Score Mean and 95% CI of Percent Change from Baseline – FAS
15.1.2.17.1	MNWS Total Score Arithmetic Least Squares Means and 95% CI – PP Set
15.1.2.17.2	MNWS Total Score Arithmetic Least Squares Means and 95% CI – FAS
TABLES	
15.2.4.39.1	Descriptive Statistics of MNWS Total Score – PP Set
15.2.4.39.2	Descriptive Statistics of MNWS Total Score – FAS

TFL number	Title
15.2.4.40.1	Analysis of MNWS Total Score – PP Set
15.2.4.40.2	Analysis of MNWS Total Score – FAS
LISTINGS	
15.3.6.13	Listing of MNWS Questionnaire Results

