15.3.6.9 Listing of ECG Data and Changes from Baseline

12.6.4.4.6 Assessment of Cough

Cough questionnaire is assessed on a daily basis from Day 0 to Day 6 and Day 30 Visit, Day 60 Visit and Day 90 Visit. Questionnaire details are reported in Section 7.3.7 “Cough Assessment”.

The number and percentage of subjects reporting a cough will be summarized by randomization arm and presented for the day prior to the assessment. The responses to the individual items, including the VAS evaluating the level of cough bother and 3 Likert scales measuring the intensity, the frequency of cough and the amount of sputum production will be listed and summarized on each day by randomization arm, for all subjects who filled in the questionnaire. The answers to the open question related to any other important observation will be listed.

The data will be presented in the below outputs:

TFL number Title

TABLES

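### Six MNWS symptom items, five of them without a cough-type safety table, are listed but never summarised by arm, although the protocol waives extra AE recording because the questionnaires will be analysed

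*SAP*

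**What the plan says.** Protocol 7.8.3 states that symptoms, or worsening symptoms, reported on a questionnaire "do not need to be documented as additional AEs because the questionnaire and the VAS will be analyzed as part of the final report". It then leaves room for judgement: "it is at the discretion of the Investigator to decide whether to document such symptoms as additional AEs". It names the face-to-face interview as the main source of AEs.

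The MNWS has 15 self-report items, each rated 0 to 4 over the previous 24 hours. On scoring, SAP 7.3.5 says: "The total score will be derived by calculating the average of all the non-missing data from the first 9 items". SAP Table 6 marks items 10 to 15 as outside the total.

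SAP 12.6.3.1.4 summarises, plots and models the total score only, for the PP Set and FAS. On the items it says: "The answers to the individual questions, along with the total score, the changes and percent changes from baseline will be listed". That listing is 15.3.6.13.

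SAP 12.1 closes off anything not named: "Summary statistics and statistical analysis will only be presented for data where detailed in this SAP".

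**The concern.** The protocol gives a reason for not recording every questionnaire symptom as an additional AE: the questionnaire will be analysed and reported. For items 10 to 15 the SAP plans no such analysis. They enter no score, table, figure or model.

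The symptoms are relevant to safety. Protocol 6.2.4 names nausea and dizziness among the signs of possible nicotine overexposure that should lead to a temporary stop in smoking. Protocol 7.3 requires the smoking abstinence (SA) arm to be monitored closely for withdrawal symptoms. Monitoring safety is a secondary objective.

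The exposed case is a symptom that a subject marks on the MNWS, does not raise at the AE interview, and that the investigator chooses not to record. It would appear in no table by arm. The study is open-label, so that choice is made by someone who knows the allocation. The MNWS asks about each symptom by name, whereas AE questions are open and non-directive. A table of the MNWS answers would therefore give a comparison between arms that does not pass through the investigator's judgement.

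**Working it through.** The plan gives no figure on this point to reproduce. The check follows each item to its planned output and then counts the responses affected.

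**Where each item goes**

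| MNWS item | In total score? | Other questionnaire table by arm | Gap |
|---|---|---|---|
| 1–9 | Yes | Not traced further: they feed the analysed total | None at score level |
| 10 Constipation | No | None | Complete |
| 11 Dizziness | No | MCEQ aversion subscale, THS 2.2 Menthol and mCC only | Partial in those arms, complete in SA |
| 12 Coughing | No | Tables 15.2.6.26 and 15.2.6.26.1, Safety Population | Negligible |
| 13 Dreaming or nightmares | No | None | Complete |
| 14 Nausea | No | MCEQ aversion subscale, THS 2.2 Menthol and mCC only | Partial in those arms, complete in SA |
| 15 Sore throat | No | None | Complete |

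Here a complete gap means that no questionnaire-based table by arm exists. It does not mean that the symptom cannot be captured as an AE.

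- Cough: SAP 12.6.4.4.6 provides the table directly: "The number and percentage of subjects reporting a cough will be summarized by randomization arm and presented for the day prior to the assessment".
- Dizziness and nausea: SAP Table 5 puts both in the MCEQ aversion subscale, and SAP 12.6.3.1.3 summarises the subscale, not the items. The questions ask whether smoking caused the symptom. On who answers, SAP 7.3.4 says: "From Day 1 onwards, only subjects who are randomized to the THS 2.2 Menthol and mCC arms will complete this questionnaire". The SA arm therefore has nothing.
- Safety outputs: the MNWS is not among the safety variables in SAP 12.6.4 or the safety tables in SAP 13.2.
- Unseen table shells: SAP 3 says that the SAP gives the list of all tables, figures and listings. No item-level MNWS table is in it.

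**How many responses**

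Inputs:
- Administrations (SAP 7.3.5): Days 0 to 6 (7) plus Days 31, 61 and 91 (3), so 10.
- Days described (SAP 12.6.3.1.4): the answers stand "for the assessment of Day-1 to Day 5, and Days 30, 60 and 90 as it is a 24-hour recall questionnaire". The Day 0 and Day 1 administrations describe Days -1 and 0, before the switch. Post-switch administrations are 5 + 3 = 8.
- Arm sizes (SAP Table 1): THS 2.2 Menthol 80, mCC 40, SA 40, total 160.

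Responses = post-switch administrations × subjects × items:

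| Group | Calculation | Responses |
|---|---|---|
| Items 10, 13, 15, all arms | 8 × 160 × 3 | 3,840 |
| Items 11, 14, SA | 8 × 40 × 2 | 640 |
| **No questionnaire table by arm** | 3,840 + 640 | **4,480** |
| Items 11, 14, THS 2.2 Menthol and mCC (partly covered) | 8 × 120 × 2 | 1,920 |
| Item 12 (covered by cough tables) | 8 × 160 × 1 | 1,280 |
| All of items 10–15 | 8 × 160 × 6 | 7,680 |

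The parts sum correctly: 4,480 + 1,920 + 1,280 = 7,680. The uncovered share is 4,480 / 7,680 = 58%.

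By arm, the 3,840 divides into 8 × 80 × 3 = 1,920 for THS 2.2 Menthol and 8 × 40 × 3 = 960 each for mCC and SA.

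**The case against.** The strongest reply is that the protocol promises analysis of the questionnaire, not a table for every item. The MNWS does get descriptive tables, ANCOVA and figures in all three arms, and every answer is listed in order of arm. Items 1 to 9, which include depressed mood and insomnia, have no item-level counts either. The MNWS is an exploratory measure of subjective effects, not a named safety endpoint.

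This narrows the point but does not remove it. Items 1 to 9 at least feed a score that is analysed; items 10 to 15 feed nothing. SAP 12.1 itself treats listings as separate from summary statistics and analysis. The exploratory label matters less once the protocol relies on the questionnaire to excuse AE recording.

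A second reply is that AEs are captured elsewhere. Protocol 7.4 requires new untoward occurrences to be documented as AEs. AE questioning is scheduled on every MNWS day, questionnaire review may prompt an AE record, and SA subjects are closely monitored. AEs are then tabulated by arm. This stands, and it limits the gap to symptoms marked on the form but neither raised nor recorded. Those symptoms are also the ones to which the waiver in Protocol 7.8.3 applies.

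Three further cautions stand in full:
- The counts include every answer of zero, so they measure scope and not harm.
- MNWS answers come from subjects who know their arm. A table would remove dependence on the investigator but not reporting bias.
- SAP 13.4 would allow a documented post-hoc table in the study report.

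**Conclusion.** The concern holds and is minor. For constipation, nightmares and sore throat in all arms, and for dizziness and nausea in SA, the SAP does not deliver the analysis that Protocol 7.8.3 gives as its reason for waiving additional AE records. The scope is up to 4,480 of 7,680 post-switch responses to items 10 to 15 (58%).

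That figure is an upper limit. It assumes 80, 40 and 40 subjects with no dropout and no missing forms. The documents do not show how many symptoms would also go unrecorded as AEs; the number could be near zero. No primary or secondary endpoint, hypothesis or analysis population is affected.

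**What to change.** Add one descriptive table to SAP 12.6.3.1.4, with a cross-reference in SAP 12.6.4:

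- **Population and layout:** Safety Population, by randomization arm and by the day assessed, with confinement (Days 1 to 5) and ambulatory (Days 30, 60 and 90) shown separately.
- **Items:** 10, 11, 13, 14 and 15. Item 12 is optional because cough is already tabulated.
- **Content:** number and percentage of subjects at each score from 0 to 4, and number and percentage with a score above baseline as defined in SAP 12.1.4.

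Leave the nine-item total score and its analysis as they are. SAP 12.6.3.1.5 already plans counts of this kind for each item of the smoking topography questionnaire, so the format exists in the plan. The cost is one extra output from data already collected, with no change to site procedures or to any planned analysis.

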**Table 6: Minnesota Nicotine Withdrawal Scale (Revised Edition) Questionnaire Scores**

	Question	Total Score
1	Angry, irritable, frustrated.	Yes
2	Anxious, nervous.	Yes
3	Depressed mood, sad.	Yes
4	Desire or craving to smoke.	Yes
5	Difficulty concentrating.	Yes
6	Increased appetite, hungry, weight gain.	Yes
7	Insomnia, sleep problems, awakening at night.	Yes
8	Restless.	Yes
9	Impatient.	Yes
10	Constipation	No
11	Dizziness	No
12	Coughing	No
13	Dreaming or nightmares	No
14	Nausea	No
15	Sore throat	No

7.3.6 Human Smoking Topography Questionnaire

Subjects will be asked by the Investigator to complete the HST questionnaire on:

- Day 0 for all subjects smoking mCC compatible with the HST SODIM® device (i.e., non-slim mCC)
- Day 4, Day 30 Visit (Day 30), Day 60 Visit (Day 60), and Day 90 Visit (Day 90) for all subjects in the THS 2.2 Menthol and mCC arms (except mCC which are not compatible with the HST SODIM® device).

The HST questionnaire has 5 items rated on a 5-point scale (from strongly agree to strongly disagree). The items are:

1. The smoking of the conventional cigarettes/products is different with the device.
2. You enjoy smoking with the device as much as without it.
3. The taste of the conventional cigarettes/products is different with the device.
4. The device is easy to use.
5. Your smoking is disturbed by the device.

7.3.7 Cough Assessment

Subjects will be asked to assess the respiratory symptom 'cough' on a VAS, on three Likert scales, and with one open ended question on a daily basis during the confinement period (from Day 0 to Day 6), and on the second day of each ambulatory period visit (Day 30 Visit, Day 60 Visit and Day 90 Visit). From Day 0 to Day 6, assessment of cough is done prior to start of product use/smoking and no later than 10:00 AM. On Day 31, Day 61 assessment of cough will be conducted irrespective of the start of product

use and not later than 10:00 AM. On Day 91 the assessment of cough will be conducted prior to smoking/product use but no later than 10:00 AM.

Subjects will be asked if they have experienced a regular need to cough, e.g., whether they have coughed several times in the previous 24 hours prior to assessment. If the answer is 'yes', subjects will be asked to complete questionnaire.

The VAS will assess how bothersome cough is to the subject ranging from 'not bothering me at all' to 'extremely bothersome', and this will be given a numeric value between 0 and 100, measured on a 100mm scale.

Subjects will also be asked to assess the intensity and frequency of cough and the amount of sputum production on Likert scales as presented in Table 7.

Table 7 : Cough Assessment Likert Scales

Question	Likert Scale
1 The intensity of cough	1 = very mild 2 = mild 3 = moderate 4 = severe 5 = very severe
2 The frequency of cough	1 = rarely 2 = sometimes 3 = fairly often 4 = often 5 = almost always
3 The amount of sputum production	0 = no sputum 1 = a moderate amount of sputum; 2 = a larger amount of sputum; 3 = a very large amount of sputum.

7.4 Human Smoking Topography Assessment

The HST SODIM® device measures and records the flow and other per-puff parameters listed below (Table 8) on Days 0, 1, 4 and the first day of each ambulatory visit. From the per-puff parameters, the per-cigarette parameters shown below will be derived (representing average values or totals per cigarette) (Table 9).

Prior to calculation of the per-cigarette parameters, the topography data will be processed through analysis software. Only data that are declared "accepted" by the software will contribute to the per-cigarette parameters and will be part of the study database.

**Table 8: HST- Per-Puff Parameters**

Description	Variable	Unit
Puff number	N_i	puff
Puff volume	V_i	mL
Puff duration	D_i	s
Average flow [V_i/D_i]	Q_{mi}	mL/s
Peak flow	Q_{ci}	mL/s
Inter puff interval	I_i	s
Sum of I_i and D_i	DF_i	s
Work [$\int P_{mi} \cdot FinalFlow \cdot dt$]	W_i	mJ
Average pressure drop	P_{mi}	mmWG
Peak pressure drop	P_{ci}	mmWG
Average resistance [P_{mi}/Q_{mi}]	R_{mi}	mmWG/ml/s
Peak resistance [P_{ci}/Q_{ci}]	R_{ci}	mmWG/ml/s

**Table 9: HST - Per-Cigarette Parameters**

Description	Variable	Formula	Unit
Total number of puffs	NPC	$\sum N_i$	puff
Total puff volume	TVOL	$\sum V_i$	mL
Average puff volume	AvgVi	$\sum V_i / NPC, i=1 \dots NPC$	mL
Average puff duration	AvgDi	$\sum D_i / NPC, i=1 \dots NPC$	s
Total puff duration	TDi	$\sum D_i$	s
Average flow	AvgQmi	$\sum Q_{mi} / NPC, i=1 \dots NPC$	mL/s
Peak flow	AvgQci	$\sum Q_{ci} / NPC, i=1 \dots NPC$	mL/s
Total inter puff interval	Tli	$\sum I_i$	s
Average inter puff interval	Avgli	$\sum I_i / NPC, i=1 \dots NPC$	s
Total smoking duration	TDFi	$\sum DF_i$	s
Total Work	TWi	$\sum W_i$	mJ
Average Work	AvgWi	$\sum W_i / NPC, i=1 \dots NPC$	mJ
Average pressure drop	AvgPmi	$\sum P_{mi} / NPC, i=1 \dots NPC$	mmWg
Average Peak pressure drop	AvgPci	$\sum P_{ci} / NPC, i=1 \dots NPC$	mmWg
Smoking Intensity	SMINT	TVOL/TDFi	mL/s
Puffing Time Index	PTI	$(100 * TD_i) / TDF_i$	%
Puff Frequency	PFeq	$NPC / (TDF_i / 60)$	puff/min

7.5 Categorical Variables

The categorical variables used in this study are shown Table 10 below. Additional categorical variables used for stratification are reported in Table 20.

Table 10: Categorical Variables Definitions

Variable	Categories
BMI (kg/m^2)	Underweight: < 18.5 Normal range: ≥ 18.5 and < 25.0 Overweight: ≥ 25.0 and < 30.0 Obese: ≥ 30.0
FTND total score	Mild: 0 - 3 Moderate: 4 - 6 Severe: 7 - 10

**Table 10: Categorical Variables Definitions**

Variable	Categories
CO breath test level (ppm)	≤ 10 > 10
COHb level	≤ 2% > 2%
Adverse event severity	Mild Moderate Severe
Adverse event relationship	Related Not related
Adverse event expectedness	No Yes
Action taken with study product due to adverse event	Product use interrupted Product use stopped Product use reduced Not applicable None
Outcome of adverse event	Death related to adverse event Not recovered or not resolved Recovered or resolved Recovered or resolved with sequelae Recovering or resolving Unknown
Seriousness Criteria	Fatal Life-threatening Requires hospitalization Results in disability/incapacity Congenital anomaly/birth defect
Severity of device event	Major Minor

8 SAMPLE SIZE JUSTIFICATION

The following discussion addresses the ability to demonstrate on Day 5 a reduction of at least 50% on four selected primary BoExps and on Day 90 on a fifth primary BoExp in smokers switching from mCC to THS 2.2 Menthol as compared to smokers continuing to smoke mCC.

Table 11 describes the expected coefficients of variation (CV) and mean ratios (MR) between THS 2.2 Menthol and the two control arms in COHb, 3-HPMA, MHBMA and S-PMA on Day 5 based on data from a controlled, randomized, open-label, 3-arm parallel single-center confinement study to investigate exposure to selected smoke constituents in smokers switching from CCs to smoking article (SMAR) cigarettes for 5 days, the YVD-CS01-EU study (ClinicalTrials.gov: ID: NCT00812279) sponsored by PMI. The mean ratios and CVs for SMAR/CC are expected to be the same as THS 2.2 Menthol/mCC.

Table 11: Coefficients of Variation (YVD-CS01-EU study)

	THS 2.2 /CC MR (CV)	THS 2.2 /SA MR (CV)
COHb	0.40 (0.32)	2.10 (0.20)
3-HPMA	0.30 (0.50)	1.70 (0.33)
MHBMA	0.15 (0.70)	1.00 (0.35)
S-PMA	0.20 (0.70)	1.15 (0.42)

Abbreviations: 3-HPMA = 3-hydroxypropylmercapturic acid; CC = conventional cigarettes; COHb = carboxyhemoglobin; CV = coefficients of variation; MHBMA = monohydroxybutenyl mercaturic acid; MR = mean ratios; S-PMA = S-phenylmercapturic acid; SA = smoking abstinence; THS 2.2 = Tobacco Heating System 2.2.

Table 12 describes the expected CV and MR between THS 2.2 Menthol and the mCC control arm in Total NNAL on Day 90 based on data from a Philip Morris USA-sponsored randomized, controlled, switching, open-label, parallel-group, single-center study in 90 male and female adult smokers evaluated six biomarkers of tobacco smoke exposure over a 12-week period (Frost-Pineda et al., 2008). The mean ratios and coefficients of variations for EHCJLI /CC are expected to be the same as THS 2.2 Menthol/mCC.

Table 12: Expected Mean Ratios and Coefficients of Variation for THS 2.2 Menthol/mCC

	THS 2.2 Menthol/mCC MR (CV)
Total NNAL	0.30 (0.60)

Abbreviations: Total NNAL = total 4-(methylnitrosamino)-1-(3-pyridyl)-1-butanol; MR = mean ratios; THS 2.2 = Tobacco Heating System 2.2.

Table 13 describes the expected CV and MR between THS 2.2 Menthol and the mCC control arm in COHb, 3-HPMA, MHBMA, S-PMA based on data from a single-center, open-label, randomized, controlled, 2-arm parallel group study to evaluate the exposure to selected smoke constituents in smoking, healthy subjects switching from CC to THS 2.1 compared to subjects continuing to smoke CC for 5 days, the ZRHX-EX-01 study (ClinicalTrials.gov: ID: NCT01780714) sponsored by PMI. The mean ratios and coefficients of variations for THS 2.1/CC are expected to be the same as THS 2.2 Menthol/mCC.

**Table 13: Coefficients of Variation (ZRHX-EX-01 study)**

	THS 2.2 Menthol/mCC MR (CV)
COHb	0.44 (0.14)
3-HPMA	0.28 (0.20)
MHBMA	0.11 (0.47)
S-PMA	0.07 (0.50)

Abbreviations: 3-HPMA = 3-hydroxypropylmercapturic acid; CC = conventional cigarettes; COHb = carboxyhemoglobin; CV = coefficients of variation; MHBMA = monohydroxybutenyl mercaturic acid; MR = mean ratios; S-PMA = S-phenylmercapturic acid; THS 2.2 = Tobacco Heating System 2.2.

Based on these two sets of assumptions on the mean ratios and coefficients of variations for the four primary BoExp on Day 5, the power to demonstrate a reduction was computed. Subjects are expected not to have any reason for exclusion from the PP Set in the confinement period for THS 2.2 Menthol arm and in ambulatory and confinement condition for the mCC arm.

Fifty percent of the subjects are expected to be excluded from the PP Set in the THS 2.2 Menthol arm in the ambulatory (mostly due to lack of compliance to the randomized product). Thus the expected populations on which the reductions will be assessed as described in Table 14.

Table 14: Sample Size to Assess the Reductions

	Sample size to assess the reduction (THS 2.2 Menthol:mCC)
COHb	80:40
3-HPMA	80:40
MHBMA	80:40
S-PMA	80:40
Total NNAL	40:40

Table 15 describes the expected power to demonstrate a reduction on all 5 primary BoExps in smokers switching from mCC to THS 2.2 Menthol as compared to those continuing to smoke mCC, using one-sided test with 2.5% type I error probability using the assumptions from YVD-CS01-EU and ZRHX-EX-01 given a sample size of 160 smokers (~80 in THS 2.2 Menthol, ~40 in mCC, and ~40 in the SA arm).

